3.3. Other Endpoints

3.3.1. Patient-Reported Outcomes (PRO)

- Change from baseline of Patient Global Assessment (PtGA) at all scheduled time points;

- Change from baseline in Dermatology Life Quality Index (DLQI) at all scheduled time points;
- Change from baseline in EuroQol Quality of Life 5-Dimension 5-Level Scale (EQ-5D-5L) at all scheduled time points;
- Change from baseline in each component (anxiety and depression) of the Hospital Anxiety and Depression Scale (HADS) at all scheduled time points;
- Change from baseline in Patient-Oriented Eczema Measure (POEM) at all scheduled time points;
- Change from baseline in Pruritus and Symptoms Assessment for Atopic Dermatitis (PSAAD) total score at all scheduled time points.

CCI
[REDACTED]

3.4. Baseline Variables

In general, for all analyses, baseline will be defined based on observations collected prior to first dose. For DLQI, EQ-5D-5L, FACIT-F, HADS, POEM, PtGA, baseline will be defined based on observations collected on or prior to the day of first dose. Baseline values for demographics, medical and other history, atopic dermatitis history will be based on measures collected at Visit 1 / Screening visit. Study Day 1 is defined as the day the subject receives first dose of study drug. For purposes of all other analyses including analyses for change from baseline, the baseline value will be defined as measured on Day 1 (before time of first dose, if time is available). If a value is missing on Day 1, then the last available observation before Day 1 will be used. For the PSAAD score, baseline will be defined as the average of all values recorded from Day -6 until Visit 2 / Day 1.

3.5. Safety Endpoints

Safety will be assessed by the spontaneous reporting of AEs, physical examinations, and clinical laboratory results in all subjects who receive at least one dose of the investigational product. Unscheduled safety assessments may be performed at any time during the study to assess any perceived safety concerns. Endpoints will be assessed as,

- Incidence of treatment emergent adverse events.
- Incidence of SAEs and AEs leading to discontinuation.
- Incidence of clinical abnormalities and change from baseline in selected clinical laboratory values, ECG measurements, and vital signs.

The safety endpoints will be defined in accordance with Clinical Data Interchange Standards Consortium (CDISC) aligned CaPS (CaPS).

3.5.1. Adverse Events

An adverse event will be considered a Treatment-Emergent Adverse Event (TEAE) if the event started during the effective duration of treatment. All events that start on or after the first dosing day and time / start time, if collected, but before the last dose plus the lag time (28 days) will be flagged as TEAEs. The algorithm will not consider any events that started prior to the first dose date.

A 3-tier approach will be used to summarize AEs. Under this approach, AEs are classified into one of 3 tiers. Different analyses will be performed for different tiers (See [Section 6.9.1](#)).

Tier-1 events: These are pre-specified events of clinical importance and are maintained in a list in the product's Safety Review Plan.

Tier-2 events: These are events that are not Tier-1 but are "common". A MedDRA Preferred Term (PT) is defined as a Tier-2 event if there are at least 4 subjects with an event in any treatment group.

Tier-3 events: These are events that are neither Tier-1 nor Tier-2 events.

3.5.2. Laboratory Data

Below is a list of hematology and serum chemistry test parameters.

- Hematology: hemoglobin, hematocrit, red blood cell count, reticulocyte count, platelet count, white blood cell count with differential, total neutrophils, eosinophils, monocytes, basophils, lymphocytes, CCI [REDACTED] coagulation panel;
- Serum chemistry: blood urea nitrogen, creatinine, creatine phosphokinase, glucose, sodium, potassium, chloride, calcium, phosphate, total bicarbonate, aspartate aminotransferase (AST), alanine aminotransferase (ALT), gamma-glutamyl transferase (GGT), bilirubin, alkaline phosphatase, lactate dehydrogenase, uric acid, albumin, total protein, total cholesterol, low-density lipoprotein (LDL), high-density lipoprotein (HDL), triglycerides.

3.5.3. Vital Signs, including Height and Weight

Vital sign measurements are oral or tympanic temperature, respiratory rate, pulse rate, and blood pressures.

Height is collected at screening and weight is collected at pre- and post-treatment.

3.5.4. Physical Examinations

Complete physical examinations consist of assessments of general appearance; skin; head, eyes, ears, nose and throat; mouth, heart; lungs; breast (optional); abdomen; external genitalia (optional); extremities; neurologic function; and lymph nodes.

4. ANALYSIS SETS

Data for all subjects will be assessed to determine if subjects meet the criteria for inclusion in each analysis population prior to unblinding and releasing the database and classifications will be documented per standard operating procedures.

4.1. Full Analysis Set

The Full Analysis Set (FAS) is defined as all subjects who have been randomized and who have received at least one dose of treatment. Subject is assigned to the randomized treatment group regardless of actual treatment received. Analyses for binary endpoints that are defined based on a threshold of change from baseline (eg, NRS4) will also require the baseline value to be equal to or greater than that threshold (eg, for NRS4, the baseline value needs to be ≥ 4). For continuous endpoint change from baseline and percent change from baseline, subjects must have baseline value to be included in the analysis.

The number of subjects randomized and dispensed study medication but did not receive treatment will be reported.

4.2. Per Protocol Analysis Set

The Per Protocol Analysis Set (PPAS) is defined as a subset of FAS who had no major protocol violations prior to Week 12 (timepoint of the primary endpoints). The subjects excluded from the PPAS will be determined and documented before the study is unblinded. The primary endpoints will be analyzed for the PPAS. This set will include subjects who:

- Had valid and non-missing baseline efficacy data (IGA, EASI).
- Met inclusion criteria 3 of documented prior qualifying treatment for AD.
- Did not permanently discontinue assigned study oral treatment prior to Week 12.
- Had actual, observed IGA and EASI scores at Week 12.
- Did not take a protocol-prohibited therapy for the primary diagnosis (high potency TCS or systemic medication or phototherapy) prior to Week 12.
- Did not take a protocol-prohibited (CYP2C19/CYP2C9 inhibitor and/or inducer drugs) concomitant medication prior to Week 12.
- Have an overall compliance of $\geq 80\%$ but $\leq 120\%$ with randomized oral treatment at Week 12.
- Adhered to standardized background topical therapy guidelines for $\geq 80\%$ of days at Week 12.

- Had no other major protocol violations that is likely to affect materially the clinical observations, or the responses of the patient determined by the clinical team before the Week 16 Analysis is conducted ([Section 5](#)).

Prior to the unblinding of the study, the clinical team may update or remove any criteria, and the final items will either be assessed by programmed checks of the data or be determined by clinical review.

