9.2. Efficacy Analysis

9.2.1. Analysis Sets

The primary analysis population for efficacy data will be the Full Analysis Set (FAS) defined as all randomized subjects receiving at least one dose of investigational product. The primary efficacy endpoint and the key secondary efficacy endpoints will also be analyzed for the Per-Protocol Analysis Set (PPAS) defined as a subset of FAS who had no major protocol violations. Major protocol violations would consist of not meeting inclusion criteria or meeting exclusion criteria or not having taken the correct randomized treatment for at least 80% of the assigned amount or not having adhered to standardized background topical therapy guidelines or having taken a protocol-prohibited concomitant medication or any other major protocol violation as determined by the clinical team or medical monitor prior to database lock. The subjects excluded from the PPAS will be determined and documented before the study is un-blinded. For all analyses, baseline value will be based on observations collected pre-dose.

It is expected that the FAS as defined here will be identical to a true intent to treat (ITT) analysis set (randomized and dispensed study medication) because the first dose is administered in-clinic. Nevertheless, any differences from ITT in terms of the number of subjects will be noted and summarized.

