The total treatment period is 20 weeks. The first part of this treatment period consists of a 16-week randomized, double-blind, placebo-controlled, double-dummy treatment period with subjects receiving both injectable and oral investigational product. The randomization and double-blind will be maintained during the final 4 weeks of the treatment period, but subjects will only receive oral investigational product. At Week 16 in the treatment period, all subjects will cease injectable dupilumab or its matching placebo. Following Week 16, subjects previously receiving only placebo will receive PF-04965842 100 mg or 200 mg QD as per their randomized allocation. Subjects previously receiving PF-04965842 100 mg or 200 mg QD will continue their respective dose. Subjects previously receiving dupilumab will continue to take oral placebo.

Eligible subjects completing the entire 20-week treatment period of the study will have the option to enter a long-term extension (LTE) study, B7451015. Subjects discontinuing early from treatment, or who are otherwise ineligible for the LTE study, will undergo a 4-week follow-up period in study B7451029.

A full schedule of activities for the study is provided in [Appendix 8](#).

Study Treatments

- Orally administered 100 mg of PF-04965842 QD with dupilumab-matching placebo administered by subcutaneous injection every other week (two injections at baseline; to dummy the loading dose) from Day 1 to Week 16, followed by orally administered 100 mg of PF-04965842 QD until Week 20.
- Orally administered 200 mg of PF-04965842 QD with dupilumab-matching placebo administered by subcutaneous injection every other week (two injections at baseline; to dummy the loading dose) from Day 1 to Week 16, followed by orally administered 200 mg of PF-04965842 QD until Week 20.
- Dupilumab 300 mg administered every other week (with a loading dose of 600 mg at baseline) with PF-04965842-matching orally administered placebo QD from Day 1 to Week 16, followed by PF-04965842-matching orally administered placebo QD until Week 20.
- PF-04965842-matching orally administered placebo QD with dupilumab-matching subcutaneously injected placebo administered every other week (two injections at baseline; to dummy the loading dose) from Day 1 to Week 16 followed by orally administered 100 mg of PF-04965842 QD until Week 20.

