6.8.3.2. Injection Dosing

Dupilumab or its matching placebo is administered every other week from Day 1 to Week 14, with two loading doses at baseline and then one dose each time.

- Exposure Time of Injection = (Last Injection Date - First Injection Date + 14); Eg, for subject receiving only the loading doses at baseline, the Exposure Time of Injection should be 14 days;

090177e1937d0b4e\Approved\Approved On: 18-May-2020 15:17 (GMT)

- Expected Number of Injections (Cumulative) will be based on Last Injection Date relative to Day 1/Baseline, using the following table:

Injection Schedule	Target Day	Window	Expected Number of Injections (Cumulative)
Baseline	Day 1	Days 1 to 7	2
Week 2	Day 15	Days 8 to 21	3
Week 4	Day 29	Days 22 to 35	4
Week 6	Day 43	Days 36 to 49	5
Week 8	Day 57	Days 50 to 63	6
Week 10	Day 71	Days 64 to 77	7
Week 12	Day 85	Days 78 to 91	8
Week 14	Day 99	Days 92 to -	9

- Eg, if a subject receives his/her last injection on Day 76, the Expected Number of Injections (Cumulative) should be 7.
- Injection Dose Compliance = (Number of Injections Received / Expected Number of Injections) * 100%.

Number, mean, standard deviation, median, minimum and maximum will be presented for those variables: Exposure Time of Injection, Number of Injections Received, Injection Dose Compliance. Number and percent will be reported for with Injection Dose Compliance <80% and Injection Dose Compliance >120%.

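### The per-protocol set screens adherence on tablets only, so in the dupilumab arm, where the tablet is placebo, no listed criterion covers missed injections

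*SAP*

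**What the plan says.** SAP Section 4.2 lists two criteria on adherence to study treatment, and both name only the oral product. One is compliance between 80% and 120% "with randomized oral treatment at Week 12". The other is "Did not permanently discontinue assigned study oral treatment prior to Week 12". No listed criterion mentions injections.

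In the dupilumab arm the injection is the active drug. SAP Section 2.2 describes that arm as dupilumab "with PF-04965842-matching orally administered placebo QD from Day 1 to Week 16".

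Protocol Section 9.2.1 words the exclusion more widely, as "not having taken the correct randomized treatment for at least 80% of the assigned amount", with no limit to the oral product.

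SAP Section 6.8.3.2 does derive an injection measure, "Injection Dose Compliance = (Number of Injections Received / Expected Number of Injections) * 100" per cent, and tabulates subjects below 80% and above 120%. Nothing links that measure to the PPAS.

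Two clauses in SAP 4.2 leave room for judgement. One criterion reads "Had no other major protocol violations that is likely to affect materially the clinical observations". A closing sentence says that before unblinding "the clinical team may update or remove any criteria".

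**The concern.** For dupilumab subjects, the listed rules judge adherence on the product that carries no drug. A subject who stopped injecting early but took every placebo tablet passes. A fully injected subject who took fewer than 80% of the placebo tablets is removed. In the two PF-04965842 arms the same rules do screen the active drug, so the filter is uneven between the arms being compared.

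SAP Section 6 plans, for all endpoints, a comparison of dupilumab with placebo and estimates among the active arms. Where the SAP leaves dupilumab out of a supportive output it says so, as in the subgroup analyses (Section 6.7) and the tipping point analysis (Appendix 3). The PPAS analyses in Sections 6.1.2 and 6.2.2 carry no such restriction. At stake is whether the PPAS estimates involving dupilumab describe subjects who actually received dupilumab.

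**Working it through.** **1. The plan's own count.** SAP 6.8.3.2 gives an example: a last injection on Day 76 implies 7 expected injections. Day 76 falls in the Days 64 to 77 window (Week 10), which the table sets at 7, so the example is reproduced. Adding the Week 12 dose gives 2 (Day 1) + 6 (Weeks 2, 4, 6, 8, 10, 12) = 8. The counts that matter are therefore 8 including the Week 12 dose, or 7 due before the Week 12 assessment.

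**2. Hypothetical dupilumab subjects who take every placebo tablet.** All have 100% oral compliance and no oral discontinuation, so all meet both listed adherence criteria.

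| Injection pattern to Week 12 | Received / scheduled | SAP 6.8.3.2 compliance |
|---|---|---|
| Day 1 syringes only | 2/8 = 25% | 2/2 = 100% |
| Stopped after Week 2 | 3/8 = 37.5% | 3/3 = 100% |
| Stopped after Week 8 | 6/8 = 75% | 6/6 = 100% |
| Missed Weeks 6 and 10, took Week 12 | 6/8 = 75% | 6/8 = 75% |

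The last column matters for the remedy. The SAP's expected count stops at the subject's own last injection, so anyone who simply stops scores 100%.

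**3. What an 80% rule on scheduled injections would require.** With 8 due: 7/8 = 87.5% passes and 6/8 = 75% fails. With 7 due: 6/7 = 85.7% passes and 5/7 = 71.4% fails. Either way, one miss is tolerated and two are not.

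**4. Size.** Let f be the share of the dupilumab PPAS that is under-injected and d the loss of response in those subjects. The fall in the dupilumab rate is f × d. The documents give no value for f, so 5-10% is an assumption. For d, assume full loss of effect, using the differences from placebo that Protocol Section 1.2.2 cites for dupilumab with topical steroids: 26 points for IGA (12% + 26 = 38%) and 46 points for EASI-75 (23% + 46 = 69%).

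- IGA: 0.05 × 26 = 1.3 points; 0.10 × 26 = 2.6 points.
- EASI-75: 0.05 × 46 = 2.3 points; 0.10 × 46 = 4.6 points.

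At f = 20% the falls would be 5.2 and 9.2 points. Partial loss of effect would give less in every case.

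**5. Which results are touched.** SAP 4.2 applies the PPAS to the Week 12 co-primary endpoints only, as supportive analyses. For these endpoints SAP Section 6 presents p-values for PF-04965842 against placebo only; comparisons with dupilumab are estimates with intervals.

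**The case against.** The gap is narrower than the listed criteria suggest. An injection not given within 7 days of its due date counts as a medication error, to be discussed for possible withdrawal, and dosing departures are recorded as protocol deviations (Protocol 5.3). Blinded review could therefore exclude a badly under-injected subject under the discretionary criterion. Safety withholding stops both products together (Protocol Appendix 4). A subject who discontinues study treatment has an end-of-treatment visit and goes into a 4-week follow-up (Protocol 6.4), so would usually lack the observed Week 12 scores that SAP 4.2 requires. Of the eight injections due by Week 12, six are given on site; only those at Weeks 6 and 10 are planned for home (Protocol 5.5). The SAP is also allowed to modify the protocol, and its version history records an update to the PPAS criteria.

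All of this stands, and it limits how many subjects are likely to be affected. It does not supply an injection threshold. Whether a given number of missed injections excludes a dupilumab subject is left to case-by-case judgement, while the tablet rule is numeric.

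A reader might infer that under-injected subjects are retained automatically. The discretionary criterion and the update clause do not support that.

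A reader might also infer that the PPAS creates a bias against dupilumab. The full analysis set holds the same under-injected subjects, so the PPAS fails to remove a dilution and does not introduce one. What stands is the unevenness: the PPAS screens active-drug adherence in the PF-04965842 arms and not in the dupilumab arm.

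**Conclusion.** The point holds in a limited form. By its listed criteria, the SAP's PPAS classifies dupilumab subjects on placebo tablets, which is narrower than Protocol 9.2.1. The consequence is confined to the supportive Week 12 estimates of dupilumab against placebo and of PF-04965842 against dupilumab, and it would tend to lower the dupilumab rate. The size in step 4 rests on an assumed share of 5-10% and on placebo-like response in those subjects; neither comes from trial data.

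Three stronger conclusions are tempting and not supported.

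- **That the trial's main claims are at risk.** The error-controlled co-primary tests compare PF-04965842 with placebo in the full analysis set. In the PPAS versions of those comparisons the tablet is the active drug, so the oral rule fits.
- **That the IGA effect could be much larger at the same share.** The cited dupilumab rate is 38%, so a loss of 40 points per subject, for example, is impossible, and the loss down to the placebo rate is 26.
- **That the Week 2 itch test against dupilumab is distorted.** SAP 4.2 does not apply the PPAS to it. Protocol 9.2.1 would, but only the two Day 1 injections fall due before the Week 2 visit, and both are given on site under supervision.

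**What to change.** Add two criteria to SAP 4.2, before unblinding:

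- no permanent stop of the injectable product before Week 12;
- injection compliance of at least 80% and at most 120%, with the injections scheduled by Week 12 as denominator. State which count is used: 8 including the Week 12 dose, or 7 due before the Week 12 assessment. Do not reuse the SAP 6.8.3.2 expected count, which would pass anyone who stops.

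Apply both to all arms. Every subject receives active or dummy injections, and membership of the set is fixed while the arms are still blinded. Then reconcile SAP 4.2 with Protocol 9.2.1, including which endpoints the PPAS covers.

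The cost is two lines of text and a derivation from injection data already collected. The PPAS becomes slightly smaller; by how much cannot be computed, because no non-compliance rate is given. Some PF-04965842 and placebo subjects will be removed for missed dummy injections, and fully injected dupilumab subjects with poor tablet compliance will still be excluded. Both follow from using one blinded rule for all arms.

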4.3. Safety Analysis Set

The Safety Analysis Set (SAF) will be defined as all subjects who receive at least one dose of study medication classified according to actual study treatment received. The safety analysis set is the primary population for treatment administration/compliance and safety. A randomized but not treated subject will be excluded from the safety analyses.

5. GENERAL METHODOLOGY AND CONVENTIONS

There will be a total of two planned analyses conducted for the study. The Week 16 Analysis will be performed after the last subject in the study has the opportunity to complete the Week 16 visit. The Week 16 Analysis will be the final analysis for the co-primary and key secondary endpoints, and the overall family-wise Type 1 error will be controlled as specified in [Section 5.1](#). The conclusions with regards to the co-primary endpoints and the secondary endpoints will be based on this analysis. The results from the Week 16 Analysis will not be used to make decisions for modifying the study design or for stopping the study. At the time of Week 16 Analysis, access to the database containing individual treatment group assignments will be restricted to the sponsor study team, while study sites, investigators and subjects will not be unblinded.

The final clinical study report (CSR) for the study will be based on the results from the Week 16 Analysis.

The End of Study Analysis will contain additional data after the final database release and the results will be reported in a supplemental CSR.

5.1. Hypotheses and Decision Rules

[figure not shown]
PF-04965842 200 mg QD will be declared superior to placebo if the null hypothesis of no difference between PF-04965842 200 mg QD versus placebo for both co-primary endpoints is rejected at the 5% significance level. Similarly, PF-04965842 100 mg QD will be declared superior to placebo if the null hypothesis of no difference between PF-04965842 100 mg QD versus placebo for both co-primary endpoints is rejected at the significance level specified below.

A sequential Bonferroni-based iterative multiple testing procedure to strongly control the familywise Type 1 error at 5% will be used for assessing each of the two PF-04965842 doses (200 mg QD and 100 mg QD) versus placebo on the primary and key secondary endpoints. The procedure belongs to a class of consonant multiple test procedures (Hommel et al. 2007) which are a subclass of the closed test procedures (Marcus et al. 1976).

The procedure will first assess the co-primary endpoints (IGA and EASI-75 at Week 12 for 200 mg QD vs placebo) at the 5% level. If this hypothesis is not rejected, then statistical significance will not be claimed for any subsequent hypotheses. If this hypothesis is rejected, then assessing for statistical significance will continue for the co-primary endpoints (IGA and EASI75 at Week 12) for the 100 mg QD vs placebo comparison. If this hypothesis is not rejected, then no statistical significance will be claimed for any subsequent hypotheses. If this hypothesis is rejected, then continue as follows:

- A series of hypotheses related to the severity of pruritus at Week 2 will be assessed at the 2.5% level in the order specified in Sequence A.
- If all hypotheses in Sequence A are rejected, then the unused alpha level of 2.5% will be passed on to the assessing for the Week 16 endpoints in the order specified in Sequence B at a 5% significance level (see figure below). The statistical significance for each hypothesis in Sequence B cannot be claimed unless the prior hypothesis in the sequence is statistically significant. In Sequence B, if one hypothesis is not rejected at alpha level of 5% then no statistically significant will be claimed for any subsequent hypotheses in the sequence.
- In Sequence A, if one hypothesis is not rejected at alpha level of 2.5% then no statistically significant will be claimed for any subsequent hypotheses in the sequence. In this case, the assessing for statistical significance in Sequence B will be at the 2.5% level. If all hypotheses in Sequence B are rejected, then the unused alpha level of 2.5% will be passed back for assessing the hypotheses in Sequence A at the 5% level. In Sequence B, if one hypothesis is not rejected at alpha level of 2.5 % then no statistically significant will be claimed for any subsequent hypotheses in the sequence.

Figure 2 Schematic for Multiple Testing Procedure

The figure above illustrates the procedure showing the sequence of the tests.

In order to be more rigorous about the onset of relief of severity of pruritus, a step-down approach with the NRS4 endpoint from Week 2 to earlier time points will be utilized as an additional family of hypothesis tests separate from [Figure 2](#) once statistical significance is demonstrated at Week 2. Rejection of each hypothesis of no difference in NRS4 at Week 2 within Sequence A will enable further assessing at earlier time points. Specifically, further hypotheses of no difference in NRS4 will be assessed along the following four sequences:

- If hypothesis of no difference in NRS4 at Week 2 between 200 mg QD and placebo is rejected in Sequence A, compare 200 mg QD versus placebo at Day 15, Day 14, Day 13, Day 12, ..., Day 2, in that order. Any hypotheses after the last time point (or Day) for which the comparison 200 mg QD versus placebo is significant will not be considered statistically significant.
- If hypothesis of no difference in NRS4 at Week 2 between 100 mg QD and placebo is rejected in Sequence A, compare 100 mg QD versus placebo at Day 15, Day 14, Day 13, Day 12, ..., Day 2, in that order. In this sequence, any hypotheses after the last time point (or Day) for which both comparisons (200 mg QD versus placebo and 100 mg QD versus placebo) are significant will not be considered significant.
- If hypothesis of no difference in NRS4 at Week 2 between 200 mg QD and dupilumab is rejected in Sequence A, compare 200 mg QD versus dupilumab at Day 15, Day 14, Day 13, Day 12, ..., Day 2, in that order. For this sequence, any hypotheses after the last time point (or Day) for which both comparisons (200 mg QD versus placebo and 200 mg QD versus dupilumab) are significant will not be considered significant.
- If hypothesis of no difference in NRS4 at Week 2 between 100 mg QD and dupilumab is rejected in Sequence A, compare 100 mg QD versus dupilumab at Day 15, Day 14, Day 13, Day 12, ..., Day 2, in that order. For this sequence, any hypotheses after the last time point (or Day) for which all four comparisons (200 mg QD versus placebo, 200 mg QD versus dupilumab, 100 mg QD versus placebo and 100 mg QD versus dupilumab) are significant will not be considered significant.

All hypotheses in each of the four sequences will be assessed at the 5% level of significance. Although this testing procedure will not protect the Type-I error for the family of all possible comparisons, it will provide Type-I error protection for the family of NRS4 time points within each treatment group and treatment groups within each time point.

Hypotheses corresponding to all secondary and other endpoints will be tested at the 5% level of significance without any adjustment for multiplicity.

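### The daily NRS4 step-down in SAP 5.1 lacks a stop at the first non-significant day, so read literally it does not give the error protection across days that the SAP asserts

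*SAP*

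**What the plan says.** SAP 5.1 adds a family of tests outside Figure 2 to describe onset of itch relief: "a step-down approach with the NRS4 endpoint from Week 2 to earlier time points will be utilized". There are four sequences: each dose against placebo and each dose against dupilumab. Each opens only if the matching Week 2 hypothesis is rejected in Sequence A. The first reads "compare 200 mg QD versus placebo at Day 15, Day 14, Day 13, Day 12, ..., Day 2, in that order", and the others use the same days. Every test is at 5%.

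The limits on claims are:

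- **200 mg versus placebo:** "Any hypotheses after the last time point (or Day) for which the comparison 200 mg QD versus placebo is significant will not be considered" to show a difference.
- **100 mg versus placebo:** the bar falls on "any hypotheses after the last time point (or Day) for which both comparisons (200 mg QD versus placebo and 100 mg QD versus placebo) are" found to be significant.
- **200 mg versus dupilumab:** the same form, with the bar after the last day on which "both comparisons (200 mg QD versus placebo and 200 mg QD versus dupilumab) are significant will not be considered significant".
- **100 mg versus dupilumab:** the same form, requiring all four comparisons to be significant.

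The section disclaims protection over all possible comparisons together, but says of the daily procedure that "it will provide Type-I error protection for the family of NRS4 time points within each treatment group" and across groups within each time point. For Sequence B the same section words the stop differently: "if one hypothesis is not rejected at alpha level of 5% then no statistically significant will be claimed for any subsequent hypotheses in the sequence". Sequence A has the equivalent sentence at 2.5%.

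**The concern.** A fixed-sequence test at full alpha controls error across its steps because testing ends at the first non-rejection. The daily sequences instead end at the last rejection. If a non-significant day can be passed over, every remaining day is a fresh 5% test.

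The output at stake is the earliest day on which a dose is said to beat placebo or dupilumab on itch. SAP 5.2 allows no claim of significance unless Section 5.1 or 6 provides for it, so these sentences are what authorises the daily claims. SAP 6 reports p-values against dupilumab only for NRS4 at Week 2 and on Days 2-15, so the same sentences govern the daily head-to-head onset claims. Gaps are plausible: SAP Appendix 2 analyses each of these days on that day's observations alone, and SAP 5.3.1 leaves intermittently missing values missing, so the number analysed can vary from day to day.

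**Working it through.** **1. Inputs.** Day 15 to Day 2 is 15 − 2 + 1 = 14 tests per sequence, each at 5% (SAP 5.1), two-sided (SAP 2.2, Sample Size Determination). The documents give no day-to-day correlation of the test statistics, so the correlations below are assumptions.

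**2. Reproducing the 5%.** With a first-failure stop, a false claim requires rejection of the first true null reached, so the error is at most P(|Z| > 1.96) = 0.05. Simulation (200,000 runs, all 14 days null, AR(1) correlation 0 to 0.95) gives 4.9% to 5.1%. The asserted protection holds under that rule.

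**3. The literal rule, 200 mg versus placebo.** Suppose Days 15-8 are significant, Days 7 and 6 are not, Day 5 is, and Days 4-2 are not.

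- Literal rule: the last significant day is Day 5. The bar covers Days 4-2, which were not significant anyway. Days 15-8 and Day 5 are claimed, and onset is Day 5.
- First-failure stop: testing ends at Day 7, and onset is Day 8.

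This is general. In simulation the literal rule removed no significant day in any run.

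**4. Size.** Take real effects on Days 15-8, always detected, and none on Days 7-2 (six null days). The literal error is P(|Z| > 1.96 on at least one of six days). The favourable part counts only Z > 1.96, the direction that makes onset look too early. From 400,000 simulated runs:

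| Assumed correlation | Equal between all days: two-sided (favourable) | AR(1): two-sided (favourable) |
|---|---|---|
| 0.5 | 20.6% (10.3%) | 23.5% (12.0%) |
| 0.7 | 16.4% (8.2%) | 20.0% (10.0%) |
| 0.8 | 13.9% (6.9%) | 17.1% (8.6%) |
| 0.9 | 10.8% (5.4%) | 13.2% (6.6%) |

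With a first-failure stop only Day 7 can open a false claim: 5.0% two-sided and 2.5% favourable at every correlation.

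**5. The linked sequences.** Take 100 mg versus placebo with 100 mg null on all 14 days. With arms of 200, 200 and a shared placebo of 100, the two comparisons correlate at (1/100) / (1/200 + 1/100) = 2/3. This case shows how the rule behaves. It is not a likely truth, because the sequence opens only after a Week 2 rejection.

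| 200 mg versus placebo | Day-to-day AR(1) | Literal rule | Unadjusted |
|---|---|---|---|
| null | 0 | 19.4% | 51.5% |
| null | 0.8 | 12.5% | 32.8% |
| strong every day | 0 | 51.2% | 51.2% |
| strong every day | 0.8 | 32.7% | 32.7% |

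With 200 mg null, the joint condition barred at least one significant day in 36% (AR(1) 0) or 24% (0.8) of runs. With 200 mg strong on every day it barred almost nothing. The joint condition is therefore a real restriction, but it weakens as the gating comparison gets stronger. The table in step 4 applies to a linked sequence when its gating comparisons are significant on every day.

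**The case against.** The best defence is that the sentence was never meant literally. The method is called a step-down, the days are tested in a stated order, and protection across time points is asserted. All of this fits if the last time point means the last day of an unbroken run, and on that reading the error is 5%. The literal reading makes the 200 mg sentence a tautology. This defence stands as evidence of intent, so a reader who infers that the sponsor chose a rule without a stop goes further than the documents allow. It does not remove the defect. The text does not say unbroken, although Sequences A and B in the same section are worded explicitly, so two readings with different onset days remain open if a gap appears.

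A reader might also infer that each of the four sequences amounts to 14 unadjusted tests, with an error near 1 − 0.95^14 = 51%. That is not supported. Three sequences carry joint conditions that bar some days. Consecutive diary days will not be independent. The Week 2 gate makes 14 true nulls unlikely.

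The scenario in step 4 can be challenged too. Protocol 1.2.4 reports that 200 mg separated from placebo in Phase 2b as early as 2 days. That was on the pruritus score, not on NRS4, but it makes six null days less likely for 200 mg versus placebo. The same fact makes a strong gate plausible for 200 mg versus dupilumab, where the joint condition would then restrict little.

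**Conclusion.** The wording is defective. Read literally, the stop sentence for 200 mg versus placebo excludes nothing, and the other three sequences exclude some days without stopping at the first non-significant one. Neither gives the protection across NRS4 time points that SAP 5.1 asserts. The disclaimer about all possible comparisons does not cover this, because the failure is within a single sequence.

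On the literal reading, in the scenario of step 4, the chance of at least one false daily claim is about 11% to 23.5% two-sided and about 5% to 12% in the favourable direction, against 5% and 2.5% with a first-failure stop. These figures rest on six null days and on assumed correlations of 0.5 to 0.9. They apply to 200 mg versus placebo, or to a linked sequence whose gating comparisons are significant every day.

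A reader might infer that the trial's main conclusions are exposed. They are not: the daily tests lie outside Figure 2, so error control for the co-primary and key secondary endpoints is unaffected. How 5% is shared between comparisons on the same day is a separate question, not assessed here.

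**What to change.** Replace the stop sentence in each of the four bullets of SAP 5.1 before unblinding.

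- For 200 mg versus placebo: *Testing proceeds from Day 15 to Day 2 and stops at the first day on which the comparison is not significant at the 5% level; no significance is claimed for that day or any earlier day.*
- For each of the other three sequences: *Significance on a given day may be claimed only if this comparison and each of the other comparisons named in this bullet are significant at the 5% level on that day and on every later day through Day 15.*

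The Week 2 gate stays as it is. The cost is four sentences, with no new data or analyses. The downside is that an isolated significant early day beyond a non-significant gap cannot be claimed. If an unbroken run was intended all along, nothing is lost.
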